8.2.3.4 Analysis of MMSE

The distribution of the MMSE at each time point of evaluation (see chapter 6) will be described on the four treatment arms separately using means and their associated standard error (a longitudinal plot will be considered). Median and range will also be computed.

Box-plots will be used to represent MMSE score distribution at baseline and at key time-points of evaluation (e.g. Baseline, 4 weeks of radiotherapy, at every 3 monthly visit where form compliance is sufficient). The proportion of patients with 'normal' and 'impaired' MMSE score will also be displayed.

Similarly to Brown et al. the changes in MMSE scores over time will be summarized in the four treatment groups by the proportion of patients with significant increase (> plus 3 points), stable (- 3 points to + 3 points) or significant decrease (> minus 3 points) of the MMSE score at the key time points of evaluation. For both questions (I and II), the distributions will be compared at each evaluation point using a Chi-square test for trend. A Bonferroni adjustment of the type I error rate will be used to correct for multiple testing.

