Statistical methods	
For the primary analysis of OS and PFS, two-sided superiority logrank tests will be computed at an overall significance level of 5%.
 
The Kaplan-Meier technique will be used to obtain estimates of the OS and PFS.
 
The Cox proportional hazard model will be fitted with the treatment and the following adjustment factors: WHO performance status (PS 0 vs >0), Age (<=50 vs >50), Presence of 1p loss (Yes vs No), Presence of oligodendroglial elements (Yes vs No). The MGMT promoter methylation status will be used as a stratification factor.
 
Changes in MMSE scores over time will be analyzed. The distributions in treatment arms will be compared at each evaluation point using a Chi-square test for trend. A Bonferroni adjustment of the type I error rate will be used to correct for multiple tests.

Central pathology Translational research	
Central pathology review will be performed.
 
Upfront assessment of 1p/19q LOH is mandatory
 
Following registration of the patient as soon as possible after surgery the following material must be sent:
 
A paraffin embedded tumor sample (preferably a tumor block, otherwise 30 unstained slides)
 
20 ml whole blood collected in an EDTA tube
 
the pathology review and 1p/19q review reports
 
Following central pathology review, central 1p/19q assessment, MGMT promoter methylation status determination and IDH mutation analysis, the H&E stained slides will be entered into the EORTC virtual tumor bank.

Quality of Life	
The main objective of QoL assessment within this clinical trial is to determine the impact of no adjuvant chemotherapy versus adjuvant therapy until progression for anaplastic glioma on overall health/QoL. Based on the recent EORTC study 26981, the hypothesis is that we expect no differences between arms using the global QOL scale during treatment, but there may be a later benefit to the adjuvant therapy arm if disease progression is achieved, thereby leading to a better global QOL.

Trial organization

- This trial is an Intergroup Trial, jointly conducted by several national/international cancer clinical research groups in different countries of European Union and third countries.
- Each participating group is the Sponsor for their participants (unless otherwise agreed).
- In summary:

Country	Recruiting group(s)	Sponsor
Canada	NCIC	NCIC
United Kingdom	MRC	EORTC
United States	RTOG	RTOG
Australia/New Zealand	COGNO CTC	COGNO CTC

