2.2 Secondary objectives

- To assess whether concurrent and adjuvant temozolomide treatment prolongs progression free survival and neurological deterioration free survival in patients with non-1p/19q deleted anaplastic glioma.
- To assess the safety of concurrent and adjuvant temozolomide in patients with non-1p/19q deleted anaplastic glioma, including late effects on cognition.
- To assess the impact of concurrent and adjuvant temozolomide treatment on the quality of life in patients with non-1p/19q deleted anaplastic glioma.

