6.4.1 Six monthly disease evaluation after the end of radiotherapy

All patients would have six monthly disease and status assessment after the end of radiotherapy.

- Physical examination including neurological evaluation
- Corticosteroid intake
- MMSE
- Quality of Life C30 and BCM20
- WHO-ECOG performance status
- Toxicity according to CTCAE v.3
- Gd-enhanced MRI or contrast CT scan of the brain
- Cognitive exam; dedicated centers only, to be carried out yearly after the start of radiotherapy (e.g., 12 months, 24 months, 36 months etc)

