7.3 Evaluation of cognitive function

Short cognitive screening with the Mini-Mental State Examination (MMSE) will take place at randomization, 4 weeks after radiotherapy and then at every scheduled follow-up visit as indicated in chapter 6. This 30-point test includes questions on orientation to time and place, registration, attention, calculations, recall, language, and visual construction. (See Appendix L)

Additional more comprehensive neurocognitive testing will be performed at dedicated centers only, as a side study to this protocol. (See Appendix I)

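### Using Holm instead of Bonferroni for the visit-by-visit MMSE tests is a small, cost-free gain; it can flag more affected visits but does not raise the chance of finding any difference

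*Combined protocol and SAP*

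**What the plan says.** Late cognitive harm is part of the safety objective: section 2.2 lists safety "including late effects on cognition". The MMSE "will take place at randomization, 4 weeks after radiotherapy and then at every scheduled follow-up visit as indicated in chapter 6" (section 7.3).

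Section 8.2.3.4 sorts each patient's change in score into three ordered groups: "significant increase (> plus 3 points), stable (- 3 points to + 3 points) or significant decrease (> minus 3 points"). For questions I and II, "the distributions will be compared at each evaluation point using a Chi-square test for trend". On multiplicity it says: "A Bonferroni adjustment of the type I error rate will be used to correct for multiple testing". The Protocol summary, under Statistical methods, plans the same. A longitudinal plot is to be considered, but no longitudinal MMSE model is planned.

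The number of tests is not given. Chapter 6 has a six-monthly schedule ("All patients would have six monthly disease and status assessment after the end of radiotherapy", section 6.4.1), while the box-plot sentence of section 8.2.3.4 gives as examples of key time points baseline, 4 weeks, and "at every 3 monthly visit where form compliance is sufficient". No overall significance level is stated for MMSE, and nothing says whether the Bonferroni divisor covers one question or both.

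**The concern.** Bonferroni applies the threshold for the smallest p-value to every p-value. Once one visit has been declared different, that is stricter than family-wise control requires. Holm orders the p-values and compares the smallest with 0.05/K, the next with 0.05/(K-1), and so on, stopping at the first failure. The error control is the same and needs no assumption about the correlation between visits.

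What is at stake is the description of timing. If temozolomide impairs cognition, readers will want to know at which visits the groups differ. With Bonferroni, some visits that Holm would flag at the same error rate are reported as not significant.

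**Working it through.** **No figure to reproduce.** The plan gives no MMSE power, effect size, decline rate, number of tests or per-test level. The inputs below marked as assumed are not in the documents.

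**Inputs.** From the documents: 748 randomized, so about 374 on each side of a question; design median survival of 27.5 and 35.5 months (section 8.1.1); three change categories. Assumed: overall level of 5% two-sided per question; exponential survival; 80% of living patients assessed at each visit; correlation between visits of 0.3, 0.6 or 0.8; decrease of more than 3 points in 10% on the reference side and increase in 8%; K = 7 (six-monthly to three years), 11 (six-monthly to five years) or 21 (three-monthly to five years).

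**Thresholds.** Bonferroni uses 0.05/K throughout: 0.0071 (K=7), 0.0045 (K=11), 0.0024 (K=21). Holm with K=11 uses 0.05/11 = 0.0045, then 0.05/10 = 0.0050, 0.05/9 = 0.0056, 0.05/8 = 0.0063, and so on. Two results follow without simulation:

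- The first Holm threshold equals the Bonferroni one, so the chance of at least one rejection is identical.
- Every later Holm threshold is larger, so anything Bonferroni rejects, Holm rejects too.

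**Size of the gain** (1,500 runs per row, planned trend test at each visit):

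| Pattern (decrease >3 points) | K | Correlation | Any rejection, Bonferroni and Holm | Mean visits flagged, Bonferroni to Holm |
|---|---|---|---|---|
| Sustained, 10% v 18% | 7 | 0.8 | 57.9% | 1.233 to 1.483 |
| Sustained, 10% v 18% | 11 | 0.3 | 62.5% | 1.067 to 1.135 |
| Sustained, 10% v 18% | 11 | 0.6 | 56.3% | 1.065 to 1.191 |
| From month 24, 10% v 25% | 11 | 0.3 | 85.3% | 2.076 to 2.239 |
| From month 24, 10% v 25% | 11 | 0.6 | 82.7% | 2.092 to 2.284 |
| From month 24, 10% v 25% | 11 | 0.8 | 73.2% | 1.937 to 2.146 |
| From month 36, 10% v 30% | 11 | 0.6 | 86.7% | 2.212 to 2.348 |
| From month 24, 10% v 25% | 21 | 0.8 | 77.6% | 2.865 to 3.115 |

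The gain in these rows runs from 0.07 visits (1.135 - 1.067) to 0.25 (1.483 - 1.233). With no effect, the family-wise error was about 3.6% to 5.0%.

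**What a longitudinal test would do instead.** Power over correlations 0.3, 0.6 and 0.8:

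| Pattern | K | Per-visit Bonferroni, any rejection | All-visit common effect | Contrast from month 24 |
|---|---|---|---|---|
| Sustained, 10% v 18% | 11 | 63, 56, 49% | 95, 81, 68% | 77, 60, 50% |
| From month 24, 10% v 25% | 7 | 82, 77, 74% | 56, 42, 35% | 98, 95, 93% |
| From month 24, 10% v 25% | 11 | 85, 83, 73% | 88, 71, 56% | >99, 97, 93% |
| From month 36, 10% v 30% | 11 | 92, 87, 84% | 75, 55, 43% | 98, 90, 82% |
| From month 36, 10% v 30% | 7 | 65, 67, 71% | 14, 10, 10% | 40, 34, 33% |

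The all-visit test wins for sustained harm and usually loses for late harm. The late contrast does well when its window fits the onset and loses when few visits in the window are affected (last row).

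**Single-visit power.** For 5% v 12% (assumed) with 300 per side, SE = sqrt((0.05×0.95 + 0.12×0.88)/300) = 0.0226 and 0.07/0.0226 = 3.10. Power is Φ(3.10 - 1.96) = 87% at 0.05, Φ(3.10 - 2.84) = 60% at 0.05/11 and Φ(3.10 - 3.05) = 52% at 0.05/22. With 150 per side the ratio is 2.19 and the powers are 59%, 26% and 19%. These show what a stricter level costs at one visit. They do not measure the gain from Holm or from a longitudinal model.

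**The case against.** The plan can fairly be defended as it stands. Bonferroni is valid and simple, the MMSE is a short screening test serving a secondary endpoint, no power is claimed for it, and Holm leaves the headline question, whether any visit differs, exactly where it was. All of that stands; it limits the size of the point but does not remove it. Bonferroni also gives simple simultaneous confidence intervals, but section 8.2.3.4 plans none for MMSE, so nothing planned is lost.

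From the other direction, a reader might infer three stronger things.

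- *That one longitudinal test over all visits should replace the per-visit tests.* Mixed models are already planned for quality of life (section 10.4) and for the neurocognitive side study (Appendix I), and such a test is clearly better for sustained harm. But the objective in section 2.2 concerns late effects, and there an average over all visits usually has less power than the present plan. Reducing the outcome to decline yes or no would also discard one of the three ordered categories.
- *That the fall from 87% to 52% is what the plan loses and a better method recovers.* Those are powers at one visit under assumed rates, not the plan's chance of a rejection at any visit.
- *That the planned comparison is biased and a mixed model cures it.* The plan states no rule for missing MMSE forms, so comparing only attenders is a reasonable reading, not a stated one. If decline itself causes the missed test, data are not missing at random and the model is biased too. Nor does that assumption deal with deaths, which the design expects to differ between the sides.

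**Conclusion.** The point holds as a small, free improvement. Holm keeps the family-wise error, is never less powerful at any visit, and can flag more of the visits at which the groups differ. It adds nothing to the chance of finding at least one difference. In the settings tabulated the gain is between 0.07 and 0.25 visits on average. That size depends on the assumed decline rates, correlation, compliance and number of visits (about 11 for six-monthly visits over five years), none of which the documents fix for MMSE. The ordering of the two methods does not depend on those assumptions.

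The planned analysis is not in error. The documents do not support calling it invalid, nor replacing it with an all-visit average.

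**What to change.** In section 8.2.3.4 and in the Statistical methods entry of the Protocol summary, name the Holm adjustment in place of the Bonferroni adjustment. Keep the per-visit trend tests on the three ordered categories. Because Holm's thresholds, like Bonferroni's, need a count of tests, state in the same sentence the overall level, which visits are tested, and whether the family covers one question or both.

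Optional supplement, not a replacement: one longitudinal MMSE model per question with a pre-specified late-window or treatment-by-time contrast, reported with its missing-at-random assumption and a sensitivity analysis for death.

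The Holm change costs two edits of wording, with no new data and no change in error control. The supplement costs one further model per question and its sensitivity analysis.

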6.2 Before treatment start: randomization step

All pretreatment physical, neurological and quality of life evaluations should be performed within 2 weeks of randomization but after the surgical procedure leading to the diagnosis of anaplastic glioma. All laboratory evaluations must be carried out within 4 weeks from randomization. The initial assessment of disease with MR or CT must be performed between the surgery and the start of radiotherapy, unless patients underwent a biopsy only in which case the pre-operative imaging is sufficient (and only a CT for radiotherapy planning is required). Radiotherapy and concomitant temozolomide should be started within 8 days of randomization.

The baseline evaluations include:

- Complete medical history
- Physical examination including neurological evaluation and vital signs
- Vital signs, blood pressure, height and weight
- WHO-ECOG performance status
- Mini mental status examination (MMSE)
- Quality of Life C30 and BCM20
- Corticosteroid intake
- Complete blood counts: hemoglobin, haematocrit, white blood cells and differential, platelets.
- Serum chemistry: sodium, potassium, calcium, creatinine, urea, glucose, ASAT, ALAT, total bilirubin, alkaline phosphatase, gamma-GT, total protein, LDH.
- Toxicity according to CTCAE v.3
- Gadolinium enhanced MRI or contrast enhanced CT scan of the brain
- Fresh frozen tumor material for translational research (optional)
- Cognitive exam (dedicated centers only)

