8.1.2 Randomization and stratifications

Patients will be centrally randomized (for practical details, see chapter on registration / randomization procedure). A minimization technique will be used for random treatment allocation stratifying by:

- Institution,
- WHO Performance Status (0 vs >0),
- Age (≤ 50 vs > 50),
- The presence of 1p LOH only (yes vs no) ,
- The presence of oligodendroglial elements (yes vs no) and
- MGMT promoter methylation status (methylated vs unmethylated vs indeterminate).

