8.2.1.5 Mini Mental State Examination (MMSE) (secondary endpoint)

The Mini Mental State Examination (MMSE) is a brief, standardized tool to grade patients' cognitive function. It is an 11-question measure that tests five areas of cognitive function: orientation, registration, attention and calculation, recall, and language. The maximum score is 30. Since its creation in 1975 by Folstein et al (Ref. 20), the MMSE has been validated and extensively used in both clinical practice and research. Following Tangalos et al. (Ref. 21) and as previously used by Brown et al (Ref. 22) a decline of more than 3 points in the MMSE score will be considered to represent clinically significant deterioration. Following Brown et al, the patient's cognitive function will be considered 'impaired' if the MMSE score is 26 or less and 'normal' if it is 27 or more. MMSE questionnaire can be found in Appendix L.

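### The only formal MMSE comparison is a trend test on three change categories, not adjusted for baseline MMSE or the minimization factors, at some cost in power

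*Combined protocol and SAP*

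**What the plan says.** Section 8.2.3.4 summarizes MMSE change as "significant increase (> plus 3 points), stable (- 3 points to + 3 points) or significant decrease (> minus 3 points". For Questions I and II, "the distributions will be compared at each evaluation point using a Chi-square test for trend", and "A Bonferroni adjustment of the type I error rate will be used to correct for multiple testing". The Protocol summary repeats the method. The means, medians, box-plots and normal/impaired proportions in the same section are descriptive.

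The cut-off comes from section 8.2.1.5: "a decline of more than 3 points in the MMSE score will be considered to represent clinically significant deterioration". The same section fixes the ceiling ("The maximum score is 30") and calls a patient "impaired' if the MMSE score is 26 or less and 'normal' if it is 27 or more".

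Sections 6.2 and 6.6 require a baseline MMSE. Section 8.1.2 states "A minimization technique will be used for random treatment allocation stratifying by" and lists institution, performance status, age, 1p loss, oligodendroglial elements and MGMT status. Section 8.2.3.2 adjusts the OS and PFS Cox models for the stratification factors. No matching statement covers MMSE.

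**The concern.** Late cognitive effects are a secondary objective (section 2.2), and cognitive deterioration is a named secondary endpoint (section 2.3.2). Section 1.2 says that a short neuropsychological test will settle whether early temozolomide raises the risk of cognitive decline. The fuller battery is a voluntary side study at dedicated centers (section 7.3, Appendix I), so MMSE is the only objective cognitive test given to every patient.

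The planned comparison leaves information unused in two ways. It reduces a 0-30 score to three levels, and it does not condition on variables that are already collected and that the survival models partly use. Both reduce the chance of detecting a true difference at any single visit. This is separate from the loss due to Bonferroni correction over visits.

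**Working it through.** **The plan's own figure.** The plan states no power for MMSE. Its OS figure reproduces: 4 × (1.960 + 0.954)² / (ln 0.775)² = 4 × 8.492 / 0.06497 ≈ 523 events, plus 11 for the interim look = 534, as in section 8.1.1. That says nothing about MMSE, so the size here has to be simulated.

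**Step 1: the ceiling.** A patient starting at 27 can gain at most 30 − 27 = 3 points, which is not more than 3. For every patient whom the plan calls normal at baseline, the increase category is unreachable and the test is in effect decline versus no decline. Baseline therefore fixes which categories are possible.

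**Step 2: baseline as a covariate, full score.** With equal variances and correlation ρ between baseline and follow-up, the variance ratio of the adjusted score to the change score is (1 − ρ²) / [2(1 − ρ)] = (1 + ρ)/2. A change-score test with 80% power at two-sided 5% has a standardized effect of 1.960 + 0.842 = 2.802. At ρ = 0.5, 2.802/√0.75 − 1.960 = 1.275, which is 89.9% power.

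| ρ | variance ratio | 80% becomes |
|---|---|---|
| 0.3 | 0.65 | 93.5% |
| 0.5 | 0.75 | 89.9% |
| 0.7 | 0.85 | 86.0% |

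The plan does not use a full-scale change-score test, so this isolates the baseline component only.

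**Step 3: simulation inputs.** From the documents: cut-offs at more than 3 points, ceiling 30, and 748 randomized (374 per side). Everything else is assumed. Scores were drawn from a bivariate normal, rounded and capped at 30.

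- Set A: 200 evaluable per side, two-sided 5%; mean/SD 28/2.5 or 27/3; correlation 0.3, 0.5 or 0.7.
- Set B: 150 or 250 per side; alpha 0.05 or 0.005 (the number of Bonferroni tests is not stated); mean/SD 28.5/2.5, 28/3 or 27/4; correlation 0.5 or 0.7; five harm patterns (uniform shift of 0.6 or 0.9 points; 10% of patients losing 5 or 8 points; 15% losing 5). This gives 3 × 2 × 2 × 2 × 5 = 120 settings.

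**Step 4: power of the planned trend test against the baseline-adjusted full score.**

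Set A:
- Uniform 0.8-point loss: 34-48% against 66-83%.
- An extra 10% of patients losing 4-10 points: 30-57% against 54-67% in five of six settings. In the sixth (28/2.5, correlation 0.7) it was 75% against 74%.

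Set B:

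| Settings | n | median gain | gain <10 | 10-30 | >30 |
|---|---|---|---|---|---|
| All | 120 | 17.5 points | 32 | 62 | 26 |
| Uniform shift | 48 | 31 | 2 | 22 | 24 |
| Concentrated harm | 72 | 12 | 30 | 40 | 2 |

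The gain was at least 10 points in 62 + 26 = 88 of 120 settings (73%). The planned test was better in 7, all with concentrated harm, by at most 8 points. Two examples at alpha 0.05:
- 28/3, correlation 0.5, 250 per side, 15% losing 5 points: 71% against 89%.
- 28.5/2.5, correlation 0.7, 150 per side, 10% losing 5 points: 64% against 59%.

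A further run at 200 per side and 5% gave gains of 34-43 points for a uniform 0.8-point shift and 1-31 points for concentrated harm.

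Type I error at nominal 5% was 4.4-5.4% for both tests in Set A. In Set B it was 4.5-5.4% for the trend test and 4.7-5.9% for the adjusted score.

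**Step 5: where the gain comes from.** In Set B, replacing the categories by the full change score gained a median of about 10 points. Adding baseline MMSE gained about 6 more (at most 15). Keeping the three categories and adding only baseline gained about 0-8 points under the Set A assumptions, about 2-8 under those of Set B and about 1-10 in the further run. For example, with 28/3, 200 per side and 15% losing 5 points, power rose from 60.4% to 67.4% at correlation 0.5, and from 83.6% to 85.1% at 0.7.

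**Not measured.** The gain from the minimization factors beyond baseline MMSE, the gain from including the other question's indicator, and the effect of death and missing visits.

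**The case against.** The strongest objection is that the two analyses answer different questions. The endpoint is development of cognitive deterioration, and section 8.2.1.5 defines that clinically as a loss of more than 3 points. A uniform shift under 1 point is well below that threshold, and low power against it is not clearly a defect. Under concentrated harm, which the cut-off is meant to catch, the advantage of the full score shrinks and sometimes reverses. This stands. It is the reason not to demote the categories to description.

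A reader might infer that the plan throws the baseline away. It does not: the outcome is change from baseline, so baseline enters by subtraction. What is missing is baseline as a covariate.

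A reader might also infer that the ceiling biases the test or hides harm. It does neither by construction. It applies to both randomized groups, a patient at 27 or more can still decline, and type I error stayed near 5%. The ceiling also affects a linear model of the score.

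Finally, MMSE is not the only cognitive information in all patients. QLQ-C30 self-reported cognition is collected too, although section 10.4 leaves it exploratory. The descriptive means with standard errors could reveal a mean shift, so it is not established that a null test would be taken as reassurance.

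**Conclusion.** The point holds as a recommended efficiency improvement to a secondary analysis. The sole formal MMSE comparison uses neither baseline MMSE nor the minimization factors as covariates, although all are collected and the OS and PFS models adjust for the latter.

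It is tempting to say that missing adjustment costs 10-30 points of power. The documents do not support that. They give no MMSE mean, SD, correlation, harm pattern, evaluable number or count of Bonferroni tests, and most of the simulated gain comes from using the full scale. What can be said, under the assumed inputs, is this:

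- Baseline added, categories kept: roughly 0-10 points gained.
- Full score with baseline: typically 10-30 points or more.
- Little or nothing, or a small loss, when harm is a large decline in a few patients and retest correlation is high.

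**What to change.** For Questions I and II:

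1. Add a model of the MMSE score at each visit on baseline MMSE, both question indicators and the stratification factors used in the Cox model (in the Protocol summary: performance status, age, 1p loss, oligodendroglial elements and MGMT status). Use robust standard errors and report the adjusted difference with its confidence interval.
2. Keep a formal comparison of the >3-point categories, because that is the plan's definition of clinically significant deterioration. Adjust it for baseline MMSE and the same factors, for example by ordinal logistic regression.
3. State which of the two is primary.
4. Date the change before any by-question MMSE analysis still to be run. Appendix M says enrolment and treatment are complete, and section 8.3.2 records a recommendation to release the adjuvant results. Any comparison already performed should therefore stay as planned, with the adjusted model labelled supplementary.

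The cost is SAP wording and slightly more analysis, with no new data. Patients without a baseline MMSE are omitted, as they already are from the change categories. Death and missing visits affect either analysis and are not solved by this change.
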